5.3 Drug Supplies

5.3.1 Formulation and Packaging

Patiromer will be provided open-label to subjects as a powder for oral suspension in packets with appropriate labeling. The individual packets will be assembled as a kit for dispensing the adequate amount of patiromer for each subject. Each packet inside an individual kit will contain either 4.2 g patiromer, 2.0 g or 1.0 g patiromer. Subject's legally authorized representative will be instructed to mix patiromer with water, apple juice, or cranberry juice. Patiromer shipped to study site should be stored refrigerated (2 – 8°C). Study subject's legally authorized representatives will be instructed to store patiromer refrigerated (2 – 8°C) for the duration of the study.

Refer to the current version of the Investigator's Brochure for a more detailed description of the investigational drug.

5.3.2 Preparation and Dispensing of Patiromer

Patiromer is for oral administration. The subject's legally authorized representative and the subject will be instructed to mix patiromer with water, apple juice, or cranberry juice. Each patiromer dose should be individually prepared under the supervision of the subject's legally authorized representative immediately prior to administration.

Patiromer should not be heated (e.g., microwaved) or added to heated foods or liquids. Patiromer should not be taken in its dry form but mixed with water, apple, or cranberry juice only. Patiromer doses should be prepared following the steps below:

- Measure the initial volume of water (or cranberry or apple juice) needed for the assigned daily dose, see Table 2, Table 3, and Table 4 for details. Pour the initial volume of the water (or cranberry or apple juice) into a cup or glass, then add patiromer and stir. Add the additional volume of the water (or cranberry or apple juice) and stir thoroughly. The powder will not dissolve and the mixture will look cloudy. Add more water (or cranberry or apple juice) to the mixture as needed for desired consistency
- Drink the mixture immediately. If powder remains in the cup or glass after drinking, add more water (or cranberry or apple juice), stir and drink immediately. Repeat as needed to ensure the entire dose is administered. Subjects and their legally authorized representative will be instructed that patiromer can be taken either with or without food

Consult the Pharmacy Manual for details on patiromer administration through an enteral feeding tube.

Table 2: Mixing Volumes for 12 – < 18 Years Age Group Patiromer Doses (4.2 g Packets)

Possible Daily Doses ^a (g/day patiromer)	Initial Volume per Dose (mL) (Step 1)	Additional Volume (mL) (Step 2)	Total Volume (mL)
4.2 (1 packet)	15	30	45
8.4 (2 packets)	15	30	45
12.6 (3 packets)	30	60	90
16.8 (4 packets)	30	60	90
21.0 (5 packets)	30	60	90
25.2 (6 packets)	30	60	90

^a Doses described include starting doses and potential escalated doses.

Table 3: Mixing Volumes for 6 – < 12 Years Age Group Patiromer Doses (2 g Packets)

Possible Daily Doses ^a (g/day patiromer)	Initial Volume per Dose (mL) (Step 1)	Additional Volume (mL) (Step 2)	Total Volume (mL)
2 (1 packet)	5	10	15
4 (2 packets)	10	20	30
6 (3 packets)	15	30	45
8 (4 packets)	15	30	45
10 (5 packets)	30	60	90
12 (6 packets)	30	60	90
14 ^b (7 packets)	30	60	90

^a Doses described include starting doses and potential escalated doses.

^b Equivalent to the adult dose of 25.2 g/day based on weight-based scaling.

Table 4: Mixing Volumes for 2 – < 6 Years Age Group Patiromer Doses (1 g Packets)

Possible Daily Doses ^a (g/day patiromer)	Initial Volume per Dose (mL) (Step 1)	Additional Volume (mL) (Step 2)	Total Volume (mL)
1 (1 packet)	2.5	5	7.5
2 (2 packets)	5	10	15
3 (3 packets)	5	10	15
4 (4 packets)	10	20	30
5 (5 packets)	15	30	45
6 (6 packets)	15	30	45
7 ^b (7 packets)	15	30	45

^a Doses described include starting doses and potential escalated doses.

^b Equivalent to the adult dose of 25.2 g/day based on weight-based scaling.

The Investigator or qualified designee will be responsible for dispensing patiromer and for documenting the date dispensed, lot number, study visit, and subject identification number on the appropriate drug accountability records at the time of dispensation.

5.3.3 Dosing and Administration of Patiromer

Subjects should arrive in the morning of the Screening Visit(s), if possible, since dosing with patiromer may be initiated on the same day as the Screening visit. Patiromer will be administered QD and doses should be taken approximately 24 hours apart. In this study, there should be a 3 hours separation between patiromer dosing and that of other oral medications; certain medications may be co-administered with patiromer at the discretion of the Investigator (see Section 5.5). Subjects and their legally authorized representative will be instructed that patiromer can be taken with or without food.

Patiromer dose titration is allowed per a protocol-specified algorithm to achieve and maintain potassium levels (measured locally) within the target range of 3.8 – 5.0 mEq/L. A description of the patiromer dose titration algorithm is provided in Section 5.2.1.

If patiromer dose requires titration, then initiation of the titrated patiromer dose should occur at the next planned administration. The last dose of patiromer for all subjects in the study will be taken on the day before the Week 26 Visit (see Appendix B).

All subjects will be provided with a Subject Dosing Diary at Day 1. Subjects and their legally authorized representative will be instructed how to document each patiromer dose and to bring back the Diary for the Investigator and/or designee to review at Day 3, Day 7 and Day 14. The Investigator and/or designee will collect the completed Diary at Day 14.

Note: If the Investigator determines a Day 3 Visit is not needed for a subject whose last screening K^+ is < 5.5 (see Section 6.2.2), then the Diary will only be reviewed at Day 7 and Day 14 Visits.

5.3.4 Compliance

Subject's legally authorized representative will be trained at the Screening / Day 1 Visit and retrained at subsequent visits regarding proper dosing and preparation of patiromer to encourage compliance.

Study staff will assess compliance at every study visit after dispensation to confirm that the subject is taking patiromer according to the protocol instructions and document compliance in the eCRF as detailed in the electronic data capture (EDC) completion guidelines. Compliance will be assessed on the basis of treatment group assignment and on the assigned patiromer dose, duration of treatment and quantity of dispensed and returned kits/packets (used and unused).

5.4 Investigational Product Storage and Accountability

The Investigator or designee will verify and acknowledge receipt of patiromer. Patiromer must be stored in a secure area under the proper storage requirements with access restricted to the Investigator or designees. No subject other than those enrolled in this specific investigation shall take patiromer designated for this clinical study. Patiromer may not be utilized for any laboratory or animal research. Patiromer dispensed to subjects must be accurately recorded on the Drug Accountability Record maintained at the Study Center. Subject's legally authorized representatives should be instructed to return all investigational product dispensed to them (used and unused kits/packets) at each study visit.

All used and unused kits/packets of patiromer will be retained at the site for Study Monitor's verification.

Patiromer should be shipped and stored under refrigeration (2 – 8°C) in a secure location.

5.5 Concomitant Medications

Information on all concomitant medications (prescription, over-the-counter, herbal and naturopathic remedies, etc.) will be collected beginning at the Screening Visit and continuing for the duration of the study (including ET) until the last study visit.

The use of magnesium supplementation is allowed during the study and should be considered for subjects whose serum magnesium is near or below the lower limit of normal.

Patiromer should be taken 3 hours before or 3 hours after administration of other concomitant medications. At the discretion of the Investigator, the following drugs may be coadministered with patiromer: allopurinol, amlodipine, amoxicillin, apixaban, aspirin, atorvastatin, cephalexin, cinacalcet, clopidogrel, digoxin, furosemide, glipizide, lisinopril, lithium, metoprolol, phenytoin, rivaroxaban, spironolactone, trimethoprim, valsartan, verapamil, and warfarin.

For subjects taking phosphate binders TID and for whom in the opinion of the Investigator one dose per day of the phosphate binder can be replaced by patiromer, patiromer may be dosed with the same meal each day and the phosphate binder dosed with two other meals each day.

In general, subjects should continue on regular doses of their usual medications, including non-steroidal anti-inflammatory drugs (NSAIDs), COX-2 inhibitors, bronchodilators and theophylline, laxatives, and contraceptives. Doses of these medications should be kept as stable as possible during the study. Medications that the Investigator deems indicated for treatment of any intercurrent illness or a pre-existing condition that do not form an exclusion criterion for participation in this study are generally allowed. If new medications for mild to moderate pain relief are required, it is preferred that NSAIDs and COX-2 inhibitors are avoided and alternatives such as acetaminophen are used.

For subjects taking medications with a narrow therapeutic index, careful monitoring is advised.

5.5.1 *Permitted Antihypertensive Medications and Medications for Heart Failure*

5.5.1.1 RAAS inhibitor Medications, Digitalis Glycosides and Diuretics

For subjects taking any RAAS inhibitor medications or diuretic medications, the dose of these medications must be stable for at least 28 days prior to Screening. The use of digitalis glycosides (such as digoxin) are permitted if the subject has been on a stable dose at least 14 days prior to Screening.

14-Day PD / Dose Finding Phase

During subject's participation in the 14-day PD / Dose Finding Phase of the study, no new RAAS inhibitor medications, digitalis glycosides or diuretics should be initiated and doses of concomitant RAAS inhibitor medications, digoxin and diuretics should not be changed. In the event that the dose of the RAAS inhibitor, digoxin or potassium-sparing diuretic needs to be adjusted during the 14-day PD / Dose Finding Phase the subject may need to be early withdrawn from the study and the Medical Monitor should be contacted prior to a final decision regarding the discontinuation of patiromer.

Recommendations regarding the timing of any medication as described in Section 5.5 should be followed to minimize the possibility of a drug interaction. Clinical response and/or blood levels where possible should be monitored as higher doses may be required during concomitant treatment with patiromer.

Long-Term Treatment Phase

During the subject's participation in the Long-Term Treatment Phase, if needed, adjustments to RAAS inhibitor medications, digitalis glycosides or diuretics are permitted. However, if the subject is prescribed non-RAAS inhibitor antihypertensive medications or non-potassium sparing diuretics every effort should be made to adjust the non-RAAS inhibitor medication or non-potassium sparing diuretics prior to adjusting the RAAS inhibitor medications or potassium-sparing diuretics.

If at any time during the study a subject develops symptomatic postural hypotension, or subject's BP is too low in the opinion of the Investigator, non-RAAS inhibitor antihypertensive treatments should either be removed, or their doses reduced before adjustments are made to the RAAS inhibitor medications for patients taking these medications. If hypotension persists after reducing or discontinuing non-RAAS inhibitor antihypertensive medications in the Long-Term Treatment Phase, it is acceptable to alter RAASi medications per the Investigator's discretion.

Recommendations regarding the timing of any medication as described in Section 5.5 should be followed to minimize the possibility of a drug interaction. Clinical response and/or blood levels where possible should be monitored as higher doses may be required during concomitant treatment with patiromer.

Increases in potassium levels may occur as early as 2 days after discontinuation of patiromer, which may be more likely in subjects who continue taking RAASi medications after stopping patiromer. In the Follow-Up Phase, an unscheduled visit may occur at the investigator's discretion for measurement of potassium level (See Section 6.5.1).

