8	Synopsis, Section 5.5.4	Use of Fludrocortisone: 
 • Fludrocortisone dose must be stable for at least 28 days prior to screening • During the 14-Day PD/Dose Finding Phase, dose adjustments to fludrocortisone should not be made • During the Long-Term Treatment Phase adjustments to fludrocortisone are permitted for safety reasons 	Fludrocortisone was not previously described in the protocol; however, this medication decreases serum potassium and could interfere with evaluation of patiromer effect, chronic use with stable doses should have minimal effect on serum potassium and thus can be allowed in these situations
98	Section 6.1	Clarification of Subject Identifier 
 • Updated “unique subject identification number” with “unique study subject identification number” 	Clarification

No.	Section(s)	Description of Changes	Rationale
10	Section 6.1.2.2, Section 6.2.6, Section 6.4, Section 7.2, Appendix A Appendix B	
Urine Pregnancy Test in the Case of Anuric Subjects:
 
 Anuric subjects may have a serum pregnancy test instead of urine pregnancy test at Day 1 	To allow anuric subjects into the study
11	Section 6.2.1, Section 6.2.4, Section 6.2.6, Section 6.4, Section 7.2, Appendix A, Appendix B	
Urinalysis in the Case of Anuric Subjects
 
 No urinalysis will be performed on these subjects 	To allow anuric subjects into the study
12	Section 7.7	
Further Clarification of Items to be Carefully Supervised by Guardian Due to Fluoride Content:
 
 Added dental rinse 	Clarification
13	Section 8.5	
Added Reference to “SMC Plan”
	Erroneously omitted
14	Section 8.6.3	
Clarification of Frequency of DSMC Meetings
 
 Added information regarding DSMC meetings after the dose expansion group of 9 subjects complete their 14-day PD / Dose Finding Phase Added information that if a subject withdraws from the study within the 14-Day PD / Dose Find Phase, the SMC determines if sufficient information is provided for DSMC review, and the DSMC meeting may be delayed if insufficient information is provided 	Clarification / erroneously omitted

RLY5016-206P
PROTOCOL AMENDMENT #4
SUMMARY AND RATIONALE FOR CHANGES

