5.5.1.2 Other Antihypertensive Medications and Medications for Heart Failure

The use of beta-adrenergic blockers (bisoprolol, sustained release metoprolol and carvedilol are the preferred beta-adrenergic blockers but are not required) and diuretics are permitted if the subject has been on a stable dose at least 28 days prior to Screening. However, recommendations regarding the timing of any medication as described in Section 5.5 should be followed to minimize the possibility of a drug interaction. For all medications, clinical response should be monitored as higher doses may be required during concomitant treatment with patiromer (see Section 5.5).

In order to control BP at any time during the study, non-RAAS inhibitor, non-potassium sparing diuretics and antihypertensive drugs that do not affect potassium levels (e.g., calcium channel blocker, alpha blocker and alpha-2 agonist) may be added or modified per the Investigator's discretion.

While every effort should be made to keep the above medications stable during the entire study, doses may be adjusted at the discretion of the Investigator. Subjects being treated with a diuretic and who are not on a consecutive daily dosing regimen and who are scheduled to take a dose of the diuretic on the day of the study visit must be instructed to take their diuretic dose after the local and

central laboratory blood has been drawn for potassium evaluation. Additional medications that are permitted to treat the symptoms or complications of heart failure are aspirin, hydralazine, and nitrates. Doses of these medications do not need to have been stable prior to screening and can be adjusted during the study.

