12.2 Ethical Conduct of the Trial

The Investigator is responsible for assuring that the study is conducted in accordance with current local and national regulations, ICH GCP guidelines, and other applicable requirements governing the conduct of human clinical trials.

The Investigator will not deviate from the protocol without prior written approval from Relypsa, except in medical emergencies. In the event of a medical emergency, the Investigator must notify the Medical Monitor as soon as possible. Any other change to the protocol must be implemented as an amendment to the protocol and must be approved by the IRB/IEC prior to implementation.

The Investigator must inform the governing IRB/IEC of all protocol changes in accordance with the IRB/IEC's established procedure. No deviation from the protocol of any type will be permitted without complying with the established IRB/IEC procedures.

If an Investigator chooses to advertise for subjects, whether in professional or consumer publications, radio, or television, all advertising must be approved by Relypsa and the IRB/IEC prior to initiation.

Financing and insurance are covered in the Clinical Trial Agreement and Clinical Trial Insurance Policy.

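### For non-potassium-sparing diuretics, Protocol 5.5.1.1 asks for no starts or changes in the 14-day dose-finding phase, 5.5.1.2 permits both for blood pressure throughout the study, and nothing says which rule governs Days 1-14.

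*Protocol*

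**What the plan says.** Protocol 5.5.1.1 has a subsection for the 14-day dose-finding phase. It states that "no new RAAS inhibitor medications, digitalis glycosides or diuretics should be initiated" and that "doses of concomitant RAAS inhibitor medications, digoxin and diuretics should not be changed". Both statements cover diuretics without distinguishing class. The next sentence sets out possible withdrawal and contact with the Medical Monitor, but for a narrower list: "In the event that the dose of the RAAS inhibitor, digoxin or potassium-sparing diuretic needs to be adjusted". No step is given for other diuretics.

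Protocol 5.5.1.2 opens by saying that beta-blockers "and diuretics are permitted if the subject has been on a stable dose at least 28 days prior to Screening". It continues: "In order to control BP at any time during the study, non-RAAS inhibitor, non-potassium sparing diuretics and antihypertensive drugs" may be added or modified as the investigator sees fit. The antihypertensives are qualified as ones without an effect on potassium, with calcium channel blockers, alpha blockers and alpha-2 agonists as examples. The following paragraph asks that the medicines already mentioned be kept stable if possible, but says "doses may be adjusted at the discretion of the Investigator". None of these permissions is limited to the Long-Term Treatment Phase.

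The primary endpoint is the change in central-laboratory potassium from baseline to Day 14 (Protocol 9.4.1; SAP 5.1.1 and 7.9.1). The design is open-label, with no comparator.

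**The concern.** On Days 1-14 the two sections give opposite answers to the same question: may an investigator start or change a non-potassium-sparing diuretic because BP is high? One site may treat 5.5.1.1 as the phase-specific rule. Another may treat 5.5.1.2 as a BP exception.

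The answer matters because the plan treats diuretics as relevant to potassium. Protocol 1.1 lists them among the options for managing hyperkalemia, though it calls the usefulness of those options limited. Section 5.5.1.2 tells subjects on a non-daily diuretic to delay a visit-day dose until the potassium blood is drawn. The sponsor's reason for the fludrocortisone stability rule, recorded in the Amendment 3 summary and cited here for its reasoning only, was that "this medication decreases serum potassium and could interfere with evaluation of patiromer effect". The same logic applies to a diuretic. If it lowers potassium, starting or increasing it before Day 14 would add to the apparent patiromer effect, and reducing or stopping it would hide some of that effect. Without a control arm, the summary cannot separate the two.

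The starting-dose review is the most exposed step, because it begins with three children per dose level (Protocol 8.6.1).

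**Working it through.** **The rules side by side, Days 1-14**

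| Action | 5.5.1.1 | 5.5.1.2 | Conflict? |
|---|---|---|---|
| Start a non-potassium-sparing diuretic for BP | Should not | May | Yes |
| Change its dose for BP | Should not | May | Yes |
| Start a potassium-sparing diuretic | Should not | Not covered | No |
| Change the dose of a potassium-sparing diuretic | Should not; possible withdrawal, Medical Monitor contact | Only if the later dose-adjustment sentence reaches every diuretic in the section's opening sentence | Arguable |

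**Search for a tie-breaker**

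- Inclusion criterion 6 (4.1) covers only the 28 days before Screening.
- Exclusion criterion 11 (4.2) does not name diuretics.
- The prohibited list (5.6) does not include them.
- Protocol 12.2 says "The Investigator will not deviate from the protocol without prior written approval from Relypsa, except in medical emergencies", but a site following 5.5.1.2 would not think it was deviating.
- SAP 4.3 names prohibited medication among the important deviations, which does not clearly cover a diuretic.
- SAP 7.5 makes extra summaries for medications of interest optional.

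Elsewhere the authors do limit permissions by phase: 5.5.1.1 and 7.1.2 tie RAAS inhibitor adjustments to the Long-Term Treatment Phase. Section 5.5.1.2 has no such limit.

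**The plan's own figure.** The exact 95% lower bound for 12/12 is 0.025^(1/12) = 0.735, which agrees with the stated 73%. The conflict does not depend on it.

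**Illustrative size.** The documents give no diuretic effect, so I assume that one child's potassium moves by d = 0.2 to 0.6 mEq/L. For the spread I borrow the SD of 0.454 reported for the maximal reduction in the adult onset-of-action study (Protocol 1.2); its use in children is also an assumption.

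- Shift in mean = d/n. For n = 3: 0.2/3 = 0.07 to 0.6/3 = 0.20. For n = 12: 0.2/12 = 0.017 to 0.6/12 = 0.05.
- 95% CI half-width = t(0.975, n-1) × 0.454/√n, which is 1.128 for n = 3 and 0.288 for n = 12.
- Shift as a share of half-width: n = 3, 0.067/1.128 = 6% to 0.20/1.128 = 18%. n = 12, 0.017/0.288 = 6% to 0.05/0.288 = 17%.

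**In-range proportion.** Entry starts at 5.1 and the target range ends at 5.0, so a child at the entry floor is 5.1 − 5.0 = 0.1 mEq/L from counting as in range (entry uses local values, the endpoint central ones). One child is 1/3 = 33 percentage points of a three-child review and 1/12 = 8.3 points of a 12-child group. The exact lower bound is 73.5% for 12/12 and 61.5% for 11/12. Any single misclassified child would have that effect, so these figures show sensitivity and are not evidence about diuretics.

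**The case against.** The best defence is that the sections can be reconciled. Section 5.5.1.1 says should, not must. Its escalation sentence names only potassium-sparing diuretics, which suggests other diuretics were meant to be handled less strictly. Section 5.5.1.2 then supplies a BP exception for exactly that other class, and its qualifier about potassium shows the authors had confounding in mind. This reading is coherent, but it is not written down, and it does not lift the bar stated just before the escalation sentence. The qualifier most naturally describes the antihypertensives, as its examples do. If it also covered diuretics, sites would have to judge which ones qualify.

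The opposite defence, that a phase-specific rule beats a general one, is equally unstated.

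The practical safeguards carry real weight. Doses must have been stable for 28 days, poorly controlled BP can exclude a child under exclusion criterion 15, concomitant medication is reviewed at each visit and listed, and all deviations are logged. The safety committee's charter is not among the documents and may require medication changes to be shown.

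A reader might infer that the conflict covers every diuretic. It does not: the BP permission is confined to the non-potassium-sparing class, and the later dose sentence reaches potassium-sparing agents only on a strained reading, given their own escalation step.

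A reader might also infer that one diuretic change could reverse a dose decision, because 8.6.1 says up-titration in all three children may suggest too low a dose. That is an example, not a cut-off. The committee also weighs baseline, target range, clinically relevant decrease and safety, and nothing in the documents shows a decision that would flip.

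**Conclusion.** The textual conflict is certain for starting or changing a non-potassium-sparing diuretic for BP on Days 1-14, and no text settles it. Following 5.5.1.2 as written would permit a co-intervention that may move potassium before an uncontrolled Day 14 endpoint.

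The consequence is much less certain. How often it would happen is unknown. On the assumed 0.2 to 0.6 mEq/L and the borrowed adult SD, one affected child moves the mean by well under a fifth of the CI half-width, so the effect on the primary summary is likely small. The three-child review is more sensitive, but a wrong decision there is a possibility and has not been shown. Severity: minor.

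**What to change.** Add to Protocol 5.5.1.2: *Until the Day 14 potassium sample is drawn, Section 5.5.1.1 prevails for diuretics; calcium channel blockers, alpha blockers and alpha-2 agonists may be used for BP. Diuretic changes needed for safety, including the low-BP provision of 5.5.1.1, remain allowed and are reported to the Medical Monitor.*

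Under SAP 7.5, flag any diuretic start, stop or dose change between baseline and Day 14 in the concomitant-medication listing and in the data given to the safety committee. The medication data are already collected (Protocol 5.5), so the flag can still be applied if enrolment has finished.

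Two further steps are best avoided. Making every such change an important deviation under SAP 4.3 would put that label on low-BP care the protocol directs and on changes 5.5.1.2 permitted. It would alter no estimate either, since important deviations are only tabulated and listed and there is no per-protocol set. Widening the withdrawal sentence in 5.5.1.1 to all diuretics would undo a distinction that looks deliberate.

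The cost is a few more Medical Monitor contacts and one BP drug class restricted for 14 days. No child leaves any analysis, so sample size and interval width are unchanged.
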